One index of neural functioning that is of particular interest for understanding outcome in schizophrenia is mismatch negativity (MMN). MMN is an event-related potential (ERP) that is elicited in response to infrequent, physically deviant tones interspersed in the repeated presentation of a standard tone [21]. MMN is thought to index automatic, preattentive information processing, as it can be elicited without directing attention to stimuli [22]. MMN has shown stable, large deficits in schizophrenia [23] that have downstream effects on more complex cognitive operations, such as verbal learning [24], social cognition [25] and social functioning [26]. MMN is often followed by P3a, another ERP component that is assumed to reflect the covert shift in attention [27]. Similar to MMN, reductions in P3a amplitude have been documented in schizophrenia [28]. MMN has never been studied within a non-pharmacological RCT. It has been studied in pharmacotherapy trials with mixed results. Some reports found that MMN is partially normalized by second-generation antipsychotic medications [29], and others did not [30]. Given the robust MMN abnormality in schizophrenia and its relationship to higher-order cognition and real-world functioning, it will be useful to ascertain whether MMN is an appropriate treatment target and can be influenced by CR.

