Subject recruitment will be coordinated through [name] ongoing studies. The availability of recruitment infrastructure, trained clinical interviewers, and cognitive remediation software will greatly facilitate the launch and conduct of the project. All subjects interested in the study will be prescreened for general inclusion and exclusion criteria by the recruiter using HIPAA compliant procedures. During the first visit (approximately 2 hours), participants will be consented and receive standardized clinical interviews to ensure diagnosis and eligibility. Participants will also receive symptom ratings of general psychiatric and negative symptoms, as well as mood symptoms. Subjects who fit selection criteria for the study will be scheduled for another visit, within 1 week of their first visit. During the second visit, (approximately 3.5 hours), subjects will be administered a comprehensive battery of cognitive, electrophysiological, and functional capacity/community functioning measures. Subjects will then be randomly assigned to one of the two cognitive remediation treatments (BFP and Cogpack) or to the control treatment (see randomization and treatment procedure below). Subjects will participate in 3 treatment sessions a week (1 hour each) for 12 weeks. After 18 treatment sessions, subjects will come back for a midpoint assessment visit (1.5 hours) in which they will be administered the electrophysiological measures again and two brief questionnaires. Upon completion of treatment, subjects will be scheduled for a post-treatment visit within 2 weeks of the last treatment session. This visit will last approximately 3.5 hours and will include the same clinical, cognitive, electrophysiological, and functional capacity/community functioning assessments that were administered prior to treatment. A urine toxicology screen will be conducted as part of each assessment visit. In the rare instance when a subject tests positive on the urine toxicology screen, he/she will be rescheduled to come back on a different day to complete the assessments. Overall, the study will consist of 4 visits (11 hours total) and 36 treatment sessions (36 hours total). Subjects will be compensated \$15/hour for the interview and testing sessions (first 2 visits, mid- and post-training visits) and \$10/hour for the treatment sessions, a rate deemed acceptable by our IRB. Funding is requested for four years of data collection (see Table 1). The IRB application will be prepared prior to the grant being funded.

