Specific Aim #1: To compare the treatment effects of bottom-up training (BFP) to top-down training (Cogpack) as well as to a control condition on neurocognition.

Specific Aim #2: To compare the treatment effects of bottom-up training (BFP) to top-down training (Cogpack) as well as to a control condition on EEG (MMN).

Specific Aim #3: To compare the treatment effects of bottom-up training (BFP) to top-down training (Cogpack) as well as to a control condition on functional capacity.

Exploratory Aims: 1) To compare the treatment effects of bottom-up training (BFP) to top-down training (Cogpack) as well as to a control condition on social cognition and community functioning and 2) to assess whether changes in MMN are associated with changes in cognition and functioning.

Primary Analyses: To make the most efficient use of our data, our primary analytical technique will be the general linear mixed model (GLMM). GLMMs account for correlations induced by repeated measures within subjects, allow for both fixed and time-varying covariates and automatically handle missing data, producing unbiased parameter estimates provided that observations are missing at random. This allows us to include all available data from all subjects in the analyses, regardless of the degree of study participation or treatment dosage received, consistent with the intent to treat framework. For each of our primary outcomes (MCCB neurocognitive composite for Aim1, MMN amplitude at Fz for Aim 2, UPSA total score for Aim 3), our core model will include group (BFP, Cogpack, control) as the between subject factor, time (baseline, end of treatment) as the within subject factor, and a group by time interaction. Our primary hypotheses correspond to the group by time interactions comparing the outcome trajectories for the two active treatments, which can be obtained as post-hoc contrasts. Such contrasts can also be used to compare each of the active

treatments to the control condition, to test for within group change and to examine the magnitudes of group differences at the end of treatment.

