Exploratory Analyses: Significant results for the primary global measures will be followed by equivalent models for the component subdomain scores to identify the primary drivers of treatment effects. Parallel models will also be fit for the exploratory analyses of social cognition and community functioning measures. To examine the relationships between MMN and cognition and functioning, we will add this EEG index as a time-varying covariate to the primary GLMM models for the other outcome domains. Although we are underpowered for a full mediation analysis, this will also allow us to obtain a preliminary indication of whether treatment effects operate through their effect on electrophysiology. Given that age, duration of illness, symptom severity, medication (indexed by CPZ units) and dosage of treatment (number of sessions) may all impact treatment response, we will also add these measures and their interactions with treatment group and time to the primary models to (i) determine whether they explain additional variation in the outcomes and (ii) obtain preliminary information about potential treatment moderators.

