Attrition and Missing Data: We plan an intent-to-treat approach, using all available data from all subjects, regardless of the degree of program participation. As noted above, our GLMM models automatically handle missing data, making the most efficient use possible of available measurements. However, with this study population there is likely to be moderate data loss (up to 20% due to attrition and EEG artifacts based on our prior experience) and we recognize the potential for bias due to differential dropout. The impact of attrition will be evaluated by comparing dropout rates in the treatment arms using chi-square tests, and by comparing baseline characteristics of dropouts with those who have outcome data. If there is evidence that attrition patterns might introduce bias into the analyses, we will perform supplementary analyses adding propensity-score adjustments to the primary models. In the propensity score framework, baseline characteristics are used to develop a predictive model for attrition (e.g., via logistic regression), and the probability of dropout is used either as a covariate or to weight the observations in the subsequent models. In essence, cases who are similar to dropouts are weighted more heavily to “make up” for others like them who dropped out. As noted above, we will also explore treatment dosage as a covariate in secondary models. Finally, scattered missing data on covariates will be handled using multiple imputation procedures.

Power Considerations

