We plan to enroll 120 subjects (n=48 for each of the two treatment conditions and n=24 for the control group) to obtain a final sample of n=96 subjects with complete data after accounting for attrition and data loss. Power calculations are conservatively based on these numbers and assume a two-sided significance level of $\alpha=.05$. We also assume a within-subject autocorrelation of $r = .7$, a value based on our experience with similar studies in the past. Our primary hypotheses all involve comparisons (parameterized as group by time interactions) among the 3 treatment groups. Our design provides over 80% power to detect overall effects as small as $f=.13$ which is sufficient to detect any pattern of changes in the three study arms for which the difference between the two most extreme groups is at least $d=.6$ at study endpoint. For the post-hoc comparison of primary interest, namely the group by time interaction examining the outcome trajectories for the two active treatment groups, this design provides sufficient power to detect an effect equivalent to a change from no difference at baseline to a difference of $d=.5$ at the post-treatment point. In addition, we note that we have over 80% power to detect within group changes from baseline to end of treatment of $d = .35$ in the active treatment groups and $d = .5$ in the control group, small to medium effects using the conventions of Cohen. For the exploratory analyses, the relationships will be assessed using the entire sample. This yields 80% power to detect a correlation of $r = .28$ between measures at any time point; power for the model with time-varying covariates will be higher due to the repeated measures.

In our pilot data, which examined performance on Cogpack training tasks in patients receiving two sessions per week over a 1 month period, we observed within group changes ranging from $d = .5$ (connect task) to $d = 2.5$ (confusion task). While these effect sizes cannot be used directly to compute power for our primary hypotheses (since they involve different measures and only a single group) they do show that patients can experience large cognitive changes over a much shorter period and with a lower intensity intervention than what is planned for this study. Since we are powered to detect small to medium effect-sizes magnitudes, we should be in a strong position even if effects are smaller on the global cognitive and functioning batteries.

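### Exploratory aim 2 asks whether MMN change goes with outcome change, but the single MMN coefficient planned for it can be significant with no such association

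*Combined protocol and SAP*

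**What the plan says.** Under Analysis Plan By Specific Aim, the second exploratory aim is "to assess whether changes in MMN are associated with changes in cognition and functioning". The Exploratory Analyses paragraph introduces the matching analysis more loosely, "To examine the relationships between MMN and cognition and functioning", and then specifies it: "we will add this EEG index as a time-varying covariate to the primary GLMM models for the other outcome domains". The core model has group, time (baseline and end of treatment) and their interaction. The same fit is also to give a "preliminary indication of whether treatment effects operate through their effect on electrophysiology". Nowhere does the plan centre MMN within patient, form a change score or adjust for baseline MMN.

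Four other places bear on this:

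- Attrition and Missing Data commits to "using all available data from all subjects, regardless of the degree of program participation".
- Research Design and Methods has patients at the midpoint "administered the electrophysiological measures again and two brief questionnaires". The MCCB and UPSA are not repeated there.
- Background and Significance motivates MMN by "its relationship to higher-order cognition and real-world functioning", without giving a size.
- Power Considerations gives 80% power for a same-time correlation of .28 and adds that "power for the model with time-varying covariates will be higher due to the repeated measures".

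**The concern.** A mixed model allows for correlated repeated measures, but it does not take the between-patient variation out of a covariate. The group and group-by-time terms remove only arm means. One MMN coefficient therefore mixes two questions: do patients with better MMN score better, and does a patient whose MMN changes also change in score? Only the second is the stated aim.

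If MMN and the outcome share a stable correlation across patients, the coefficient can be significant although no patient's MMN change goes with an outcome change. It could then be reported as MMN change tracking cognitive change, and carried into the definitive trial that this study is meant to inform. The opposite error is also possible: a real change-change association is diluted when the between-patient slope is small. Patients with baseline data only supply purely between-patient information and move the coefficient further from the aim. Because the outcomes are measured at two visits, each patient contributes at most one outcome change.

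**Working it through.** **Inputs from the documents.** Two-sided α = .05 (Statistical Plan). 96 patients with complete data, 120 enrolled as 48/48/24, within-subject correlation .7, detectable r = .28 (Power Considerations). The arm projections of 38, 38 and 19 sum to 95, so arms of 38/39/19 were simulated to reach 96.

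**Assumed.** Correlation of .7 between visits for MMN as well, since the plan's .7 is not specific to MMN. The same-visit correlation r between MMN and outcome is not given, so a range is shown. Its sign does not matter for the two-sided test.

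**1. The plan's own figure.** Fisher z with n = 96: atanh(.28) × √93 = .2877 × 9.644 = 2.774, and Φ(2.774 − 1.960) = .792. The noncentral t gives .807. The stated 80% at r = .28 reproduces, for a correlation at one time point.

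**2. What the single coefficient estimates.** Scale both measures to variance 1 and split each patient's two values into (sum)/√2 and (difference)/√2. The variances are 1 + .7 = 1.7 and 1 − .7 = .3. The coefficient weights the two slopes by MMN variance over residual outcome variance: 1.7/1.7 for between and .3/.3 for within when r = 0. Each weight is .50.

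**3. Zero change-change association, r = .28.** A stable component alone must give r = .7 × (latent correlation), so the latent correlation is .28/.7 = .40 (and .4/.7 = .57 for r = .4).

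- Between slope = 2 × .28/1.7 = .329; within slope = 0.
- The fitted coefficient b settles at .174. Residual variances: between, 1.7 − 2(.174)(.56) + .174²(1.7) = 1.557; within, .3(1 + .174²) = .309.
- Weights: 1.7/1.557 = 1.092 and .3/.309 = .971. The between share is 1.092/2.063 = .53, and .53 × .329 = .174.
- SE ≈ 1/√(93 × 2.063) = .072; z = .174/.072 = 2.42; Φ(2.42 − 1.96) ≈ .68.

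Simulation of the planned model (REML, compound symmetry, 10,000 trials) gives .663, and .666 in a second run.

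**4. Over the range of r, with zero change-change association (% significant):**

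| r | One MMN term, 96 completers | Deviation term | One MMN term, 120 patients with 24 baseline-only |
|---|---|---|---|
| 0 | 5 | 5 | 5 |
| .1 | 13 | 5 | 16 |
| .2 | 39 | 5 | 47 |
| .28 | 66–67 | 5 | 77 |
| .4 | 94 | 5 | 98 |

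The deviation term also stays at 5% in the 120-patient case. At r = .28 with 96 completers, the single term is significant in 57% of trials if MMN reliability is .5 and 76% if it is .85. A separately coded simulation with arms 38/38/20 gave 12, 40, 67 and 95% at r = .1, .2, .28 and .4.

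**5. Reverse error: true change-change correlation .28, 96 completers.** The deviation term has about 79% power throughout. The single term has:

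- 52% if the person means are uncorrelated;
- 64% if the latent stable components are uncorrelated;
- 80, 85 and 92% at a between-patient slope of .12, .15 and .20;
- 97% if the two slopes are equal.

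**6. Mechanism reading.** Suppose BFP and Cogpack differ by .5 SD in MMN change (assumed). Adding the single term then shrinks the group-by-time effect spuriously by .5 × b, which is .03, .06, .09 and .13 SD at r = .1, .2, .28 and .4. With the deviation term the shrinkage is 0.

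**The case against.** The plan does not say that MMN goes in raw, and its introductory clause speaks of relationships in general, for which a blended coefficient is legitimate. The analysis is exploratory, the plan concedes that it lacks the power for formal mediation, and it puts weight on not overlooking potentially useful findings. The false-positive rates depend on a correlation that the documents never give: at r = 0 there is no problem, and .28 is a detectable value, not an expected one. The 120-patient figures take every projected loss to be baseline-only, although the plan will ask those who stop treatment for a final assessment and its 20% also covers EEG artifacts. The plan also has an imputation rule for scattered missing covariates.

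Much of this stands as a limit on size. The percentages are conditional, and the 120-patient column is an extreme case. The power cost is real: the split loses whenever the between-patient slope exceeds about .12 in the same direction. It does not remove the mismatch. An index added as a covariate is one term with one coefficient, and no other analysis addresses change. The broader introductory clause leaves the aim as worded without a test. The imputation rule is compatible with the split if it is applied first.

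**Conclusion.** The concern holds. Followed as written, the model does not answer exploratory aim 2. With no change-change association, its MMN coefficient is significant in 13 to 94% of trials as r runs from .1 to .4, against 5% for a within-patient term. This rests on 96 completers, two visits, a .7 visit-to-visit correlation for both measures, and a stable correlation whose size the documents leave open. The algebra is firm; the practical size is not.

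The stakes are limited. The primary contrasts for Aims 1–3 are untouched, and the mechanism indication is biased only if the arms also differ in MMN change. The sentence saying that power will be higher is not wrong for the blended coefficient. What is missing is a power statement for the change-change question.

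**What to change.** In Exploratory Analyses, enter MMN as two terms: the patient's mean over baseline and end of treatment, and the deviation from that mean at each visit. For a patient with one visit, the mean is that value and the deviation is 0. Where the plan's imputation rule for missing covariates applies, impute before forming the two terms. Read exploratory aim 2 and the mechanism indication from the deviation term, and report the mean term as a between-patient association.

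In Power Considerations, keep the existing sentence for the blended coefficient. Add that, for the change-change question, a correlation of .28 with 96 pairs has about 80% power, with no gain from the repeated measures.

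The cost is one derived variable and two sentences, with no new data. Power at .28 is about 79% rather than 97% if the slopes are in fact equal. Patients with MMN at one visit only do not inform the deviation term unless the missing value is imputed.

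### The exploratory models treat number of sessions attended as a covariate and potential moderator although it arises after randomisation, so the dose and dose-adjusted estimates are open to confounding; the primary analysis is unaffected.

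*Combined protocol and SAP*

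**What the plan says.** The planned dose is common to all arms: "Subjects will participate in 3 treatment sessions a week (1 hour each) for 12 weeks" (Research Design and Methods).

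The primary model contains no dose term: "our core model will include group (BFP, Cogpack, control) as the between subject factor, time (baseline, end of treatment) as the within subject factor", plus their interaction (Primary Analyses). It uses all subjects "regardless of the degree of study participation or treatment dosage received, consistent with the intent to treat framework".

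Dose appears in two later places.

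- **Exploratory Analyses.** Attendance closes a list of otherwise patient-level clinical variables, with the statement that "dosage of treatment (number of sessions) may all impact treatment response". The plan then says "we will also add these measures and their interactions with treatment group and time to the primary models". The two aims are to see whether these variables explain further outcome variation and to "obtain preliminary information about potential treatment moderators".
- **Attrition and Missing Data.** Referring back, the plan says "we will also explore treatment dosage as a covariate in secondary models".

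Neither place separates variables fixed before randomisation from those that arise after it, and neither names a method for confounding of dose with outcome. The propensity scores in the attrition section model dropout from baseline characteristics, not dose.

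**The concern.** A treatment moderator should be fixed before assignment, so that randomisation balances it across arms. Number of sessions is not. With 36 sessions assigned to everyone, its variation comes from what happens to patients after assignment.

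The documents themselves point to causes that attendance and outcome could share:

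- **Motivation.** The Cogpack description names intrinsic motivation and perceived competency as influences on response to treatment. Motivation plausibly affects attendance too.
- **Illness course.** In the multi-session pilot, one of six patients stopped after 2 of 8 sessions because of hospitalisation.
- **Early stoppers.** Patients who discontinue treatment are asked back for a final assessment, so low-dose patients contribute endpoint data.

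Two outputs are at risk. The sessions-by-time term may show a dose-response that is only selection. And a group-by-time effect adjusted for sessions is no longer the randomised comparison: if attendance differs between programs, the adjustment can move the estimate up or down.

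**Working it through.** **Inputs from the documents.** 36 sessions in each arm (3 × 12); 96 subjects with data after 20% loss (120 × 0.8), or 38/38/19 by arm; within-subject correlation .7; two-sided α = .05, uncorrected.

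**Assumed inputs.** The documents give no attendance distribution and no attendance-outcome correlation. I assume that sessions have no causal effect and that one factor, not in the model, correlates a with sessions and a with change. The induced correlation between sessions and change is then a². With two time points and complete data, the sessions-by-time term is the slope of change on sessions.

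**Step 1: check the formula on the plan's own figure.** Power for a correlation r is approximately Φ(atanh(r)·√(n−3) − 1.96) + Φ(−atanh(r)·√(n−3) − 1.96). Power Considerations states 80% at r = .28. With n = 96, atanh(.28)·√93 = 0.288 × 9.644 = 2.77, giving 0.79. The figure reproduces.

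**Step 2: apply it to the spurious correlation.**

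| a | a² | atanh(a²)·√93 | Chance of p < .05 | Simulation, 20,000 trials |
|---|---|---|---|---|
| .3 | .09 | 0.87 | 14% | 14.1% |
| .4 | .16 | 1.56 | 34% | 33.9% |
| .5 | .25 | 2.46 | 69% | 69.7% |

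A second simulation, with the three arms (38/38/19) and group terms in the model (4,000 trials), gave 13% at a = .3 and 68% at a = .5, against 5% with no shared factor.

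**Step 3: the moderator (dose-by-group) test.** In the three-arm simulation this test stayed near 5% when the attendance-prognosis link was equal across arms. With the factor correlated .5 with change, and its correlation with sessions differing by arm, rejection was:

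- 9% for .5 in one arm and .2 in the other two;
- 16% for .7 and .2;
- 29% for .7 and 0.

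**Step 4: the dose-adjusted group effect.** The SD of change is √(2(1 − .7)) = 0.775 in outcome SD units. With both correlations .5, the within-arm slope per SD of sessions is .5 × .5 × 0.775 = 0.194. If mean attendance differs between the active arms by 0.5 SD, adjustment shifts the estimate by 0.194 × 0.5 = 0.097. A true difference of 0.50 then becomes about 0.40 or 0.60, depending on which arm attends more. The simulated values were 0.41 and 0.59. With equal mean attendance the adjusted estimate stayed at about 0.50.

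**The case against.** The strongest defence is that these are supplementary models. They sit under an exploratory heading, are called secondary in the attrition section, and are described as preliminary. The randomised contrast is estimated without dose and is still reported. All of that stands, and it limits the point to the dose findings. It does not answer the point, because an exploratory label covers multiplicity and imprecision but not bias.

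Other objections that stand in part:

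- **The first aim is associational.** Asking whether sessions explain further variation is legitimate if it is reported as an association. This is a reason to separate and label the analysis rather than forbid it.
- **The correlations in the illustration are assumed.** The listed age, illness-duration, symptom and medication terms may also remove part of the confounding. The documents therefore support saying the estimates are open to confounding, not that they will be confounded.
- **Motivation is measured.** An intrinsic motivation inventory is given halfway through training. It is not among the listed covariates, however, and is itself a post-randomisation measure.

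A reader might also infer three stronger points that the documents do not support:

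- **That the plan will use these models to pick moderators for a definitive trial.** The Statistical Plan describes the study as a whole as preparing for a definitive study, through intervention components and measures. The moderator sentence makes no such link.
- **That dose adjustment is the remedy for attrition.** The stated remedy is propensity-score adjustment; the dosage sentence refers back to the exploratory models.
- **That 14% to 70% is the false-positive rate for moderation.** Those figures apply to the sessions-by-time slope alone.

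**Conclusion.** The concern holds for the exploratory and secondary models. Number of sessions is a post-randomisation variable handled like a baseline moderator, and no section addresses the resulting selection.

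The phrase about adding terms to the primary models might suggest that the primary result is compromised. It is not: the core model is group, time and their interaction, fitted by intent to treat. No sample size or power figure changes.

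The size of the bias cannot be known from the documents. Under the assumed correlations of .3 to .5, with no true dose effect and no adjustment for the shared factor, the sessions-by-time term is falsely significant in about 14% to 70% of trials. The dose-by-group test is inflated only if the attendance-prognosis link differs by arm. The dose-adjusted group effect is shifted only if mean attendance also differs. This is a minor point about what the exploratory analyses can support.

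**What to change.** 1. In Exploratory Analyses, limit the covariate and moderator models to baseline values: age, duration of illness, baseline symptom severity and baseline CPZ-equivalent dose. Remove number of sessions and its interactions, and amend the matching sentence under Attrition and Missing Data.
2. Report sessions attended by arm descriptively.
3. If a sessions-outcome association is still wanted, fit it in a separate model and report it as a non-causal association, not as moderation or as a dose-adjusted treatment effect.
4. An estimate using random assignment as an instrument is optional. It must state its exclusion assumption, that assignment affects outcome only through sessions of the assigned program. That could fail if attendance, and with it non-specific contact, differs by arm. In its simple linear form it divides the active-versus-control effect by the difference in mean program sessions. It therefore rescales that effect and gives no dose-response. It also leaves out BFP versus Cogpack and relies on about 19 control completers.

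The cost is a few lines of SAP wording and the loss of a dose-adjusted treatment estimate.
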